INTRAOPERATIVE ASSESSMENT	ERROR! BOOKMARK NOT DEFINED.

IMMEDIATE POST OP ASSESSMENT (ON REMOVAL OF SPECULUM).....**ERROR! BOOKMARK NOT DEFINED.**
10-MINUTE POST OP ASSESSMENT**ERROR! BOOKMARK NOT DEFINED.**
30-MINUTE POST OP ASSESSMENT**ERROR! BOOKMARK NOT DEFINED.**
DISCHARGE ASSESSMENT**ERROR! BOOKMARK NOT DEFINED.**
24 HOURS POST-PROCEDURE MEASURES.....**ERROR! BOOKMARK NOT DEFINED.**
QUALITY OF RECOVERY SURVEY [3].....**ERROR! BOOKMARK NOT DEFINED.**

Project Summary

Justification for the project

One half of all pregnancies among American women are unintended, with nearly 4 in 10 ending in pregnancy termination by abortion [22]. Elective abortions are among the most common outpatient surgical procedure, with an estimated 46 million performed worldwide annually. The management of pain is critical to patient care throughout the abortion experience since the vast majority of women will experience pain with the procedure [23]. Patients are most affected by pain during paracervical block, cervical dilation, suction aspiration, and post operatively with uterine cramping [24]. Innovation in pain control and reduction of anxiety, nausea and vomiting using a low cost, well-tolerated intervention could impact thousands of women each year.

Proposed research

We plan a randomized controlled trial of gabapentin 600 mg compared to placebo given 1-2 hours pre-operatively in conjunction with perioperative paracervical block for surgical abortion. We hypothesize that adding gabapentin to local anesthesia will reduce perioperative and post-operative pain associated with surgical abortion. Additionally, we hypothesize that gabapentin will reduce nausea, vomiting, anxiety, and consumption of pain medication.

New features

The use of gabapentin in the setting of abortion has never been evaluated. Its use in similar surgical settings as an adjunct to pain management regimens has proven to be beneficial. It is generally well tolerated, inexpensive, has minimal side effects, and few contraindications.

Problems anticipated

The high volume at our clinic will benefit our recruitment efforts. However the coordination of this study may potentially disrupt clinic flow. We will limit our daily recruitment to reduce clinic impact. Post-operative follow-up may be challenging, thus to reduce the impact of loss to follow-up, most of our outcomes are measured on the same day as the procedure. Further, multiple contact approaches will be employed and a second incentive offered after completion of the post-operative assessment.

1. Description of the Project

1.1 Rational and objectives of the study

1.1.1 Rationale

Surgical abortions in North America are typically performed using local anesthesia, oral analgesics, moderate sedation, or a combination of approaches. A 2009 Cochrane review of pain control during abortion concluded that evidence on paracervical block (PCB) alone in reducing abortion related pain was limited, while the addition of ibuprofen and naproxen can slightly reduce intraoperative and post-operative pain [1]. Evidence supports the benefit of IV sedation (moderate or deep) at reducing intraoperative and post-operative pain with abortion.[2] However, IV sedation may not be an option for all women or in all clinical settings. Other recently examined adjuncts to pain control have not proven to be beneficial at reducing abortion-related pain [3-5].

Gabapentin is widely used to treat neuropathic and chronic pain. The mechanism of action may include calcium channel blockade or modulation of nociceptive neurotransmitters. Clinical trials support the use of perioperative pregabalin and gabapentin to reduce perioperative and post-operative pain in a variety of clinical settings, for both major and minor surgical procedures [6, 7]. While pregabalin has a faster peak plasma concentration, gabapentin is a less expensive option with peak concentration reached by 2 hours, with substantial evidence to support routine use and safety in reducing perioperative pain.

Innovation in pain control and reduction of anxiety, nausea and vomiting using a low cost, well-tolerated intervention could impact thousands of women each year who undergo common outpatient gynecologic procedures. We propose a novel use of oral gabapentin administered in conjunction with local anesthesia via PCB for surgical abortion. The use of gabapentin in the setting of abortion has never been evaluated; however it is used routinely and successfully in several similar surgical settings as an adjunct to pain management regimens. It is generally well tolerated and inexpensive, with minimal side effects and few contraindications [8]. When used in other gynecologic settings, gabapentin

has been shown to improve pain scores, and reduce nausea and vomiting [14,15]. If effective, this simple adjunct to current pain regimens could expand options for the management of women undergoing surgical abortion. We believe that the addition of gabapentin given prior to the procedure will reduce intraoperative and post-operative pain. Other secondary outcomes such as nausea, vomiting, and anxiety influence a woman's ability to return to her normal baseline level activity and her experience of abortion in general. The addition of gabapentin to current analgesia may provide an option to improve a woman's experience during a surgical abortion. Gabapentin 600mg was selected as a well-tolerated intermediate dosage with benefit proven in prior preoperative studies. Multiple post-operative doses in addition to the pre-operative dose had no significant effect on VAS scores at 24 hours, thus favoring single dosage [9].

1.1.2 Objectives and hypotheses

Pain control during and after abortion is a family planning research priority, as identified by the Society for Family Planning [10]. Pain management regimens for surgical abortion may include: local anesthetic, oral analgesics, moderate sedation, deep sedation, or a combination of approaches. While several recent studies have evaluated supplemental medications or therapies intended to reduce abortion-related pain, such as non-steroidal anti-inflammatory drugs (NSAIDs), narcotics, anxiolytics, misoprostol, nitrous oxide, or music, most have failed to note improved pain scores. Optimal pain management has yet to be established as many women continue to report moderate to severe pain during and after an abortion procedure [11].

We hypothesize that adding gabapentin pre-operatively to local anesthesia will reduce perioperative pain associated with surgical abortion. Additionally, we hypothesize that pre-operative gabapentin will reduce perioperative nausea, vomiting, and anxiety, as well as reduce post-operative pain and consumption of pain medication with few adverse effects.

Primary Aim: To evaluate the impact of adjunctive pre-operative gabapentin on intraoperative pain scores (at time of evacuation with the start of suction) during surgical abortion.

Secondary Aims:

- To evaluate the impact of pre-operative gabapentin on pain scores post operatively (removal of speculum, 10 and 30 minutes after procedure, at time of discharge and 24 hours after procedure)
- To evaluate the impact of pre-operative gabapentin on:
 - Perioperative nausea and vomiting
 - Perioperative anxiety
- To evaluate the impact of pre-operative gabapentin on perioperative medication consumption, and pain medication consumption up to 24 hours after the procedure
- To evaluate safety of gabapentin in this setting (monitor side effects or adverse events of gabapentin in this setting)

1.2 Previous similar studies

There have been multiple studies evaluating pain control during first trimester abortion under local anesthesia. Paracervical block (PCB) alone does not provide optimal pain control for all women. Further, studies evaluating different concentrations of lidocaine or different methods of injection did not significantly reduce pain. Pain with aspiration does not differ when comparing 0.5% lidocaine with 1% lidocaine [1]. Aspiration-related or post-operative pain does not differ when comparing a four site paracervical block (3,5,7,9 o'clock positions) to a two site block (4 and 8 o'clock positions) [12]. Non-steroidal anti-inflammatory drugs (NSAIDS) may be helpful in reducing pain for women receiving an abortion with PCB. Ibuprofen 600 mg given 30 minutes prior to dilation and curettage slightly improved intraoperative pain scores with a mean pain difference of 7.8 mm (on 100-mm scale) between the ibuprofen and placebo groups, but showed a more significant improvement (mean pain difference of 9.3 mm) in pain scores post-operatively [13]. The clinically meaningful significance of this difference is questionable. Naproxen given 1-2 hours prior to surgery has also been shown to improve pain scores [1]. Although NSAIDs

may improve pain with PCB, pain control is still often inadequate and some women may not be able to tolerate NSAIDs as they may develop gastrointestinal distress when given. Intravenous (IV) moderate sedation has been shown to offer superior perioperative and post-operative pain control [1, 14] compared to local anesthesia with PCB; however, patients may not be able to receive IV sedation due to the clinical setting, inability to find a means of transportation post-operatively, or may find IV sedation unacceptable.

We propose a novel regimen of oral gabapentin administered in conjunction with local anesthesia via PCB for surgical abortion. Gabapentin is used to treat neuropathic pain. Clinical trials support the use of perioperative gabapentin to reduce perioperative and post-surgical pain in a variety of clinical settings [6]. Gabapentin is well-tolerated and inexpensive, with mild, if any, side effects [8]. In a systematic review of 22 randomized controlled trials (RCT) of multiple surgical procedures including ambulatory nasal surgery, orthopedic procedures and laparotomy, a single pre-operative dose of gabapentin significantly reduced 24-hour opioid consumption [8]. Of the studies evaluating gabapentin use, 13 included a single dose of gabapentin, with doses ranging from 300-1200mg administered 1-2 hours prior to surgery with results noting a 20-62% reduction in opioid consumption within 24 hours after the procedure [8]. In the setting of obstetrics and gynecology, evidence supports perioperative gabapentin before hysterectomy to reduce pain scores, nausea, and vomiting [9, 15]. Following hysterectomy, the pain intensity difference between the control and gabapentin group was greatest in the early postoperative period, and decreased after 12 hours. The dosages ranged from 400mg - 1200mg, and the timing of dosing varied (preoperative dose, followed by multiple dosing at interval times identified)[8]. In addition, VAS scores at 24 hours decreased from 9-42.7 to 2-25.3 mm [9]. This study additionally found the significant reduction in VAS score was only noted with pre-operative administration while additional dosing was not associated with significant changes when compared to placebo. Further, postoperative nausea and vomiting was also decreased by pre-operative administration of gabapentin. However this may be due to decreased opioid consumption [9].

Preoperative gabapentin prior to cesarean delivery improved pain scores at 24 hours with less need for post-operative analgesia compared to placebo [15]. A randomized

trial in the setting of cesarean delivery showed improved pain scores and decreased pain medication requirements with a 600 mg dose of pre-operative gabapentin [15]. In this study, patients presenting for scheduled cesarean delivery were randomized to gabapentin or lactose placebo given 1 hour preoperatively. Pain scores with movement were evaluated at 24 hours, with the gabapentin group reporting pain scores of 21 mm (95 % CI 13-28) and the placebo group reporting scores of 41 mm (95% CI 31-50). Further, the gabapentin arm had higher maternal satisfaction scores [15].

In an outpatient setting similar to surgical abortion, perioperative gabapentin has been shown to decrease post-operative opioid consumption and anxiety for minor orthopedic procedures and hemorrhoidectomy [16, 17]. One randomized trial evaluated gabapentin 600 mg at 2 hour(s) prior to arthroscopic anterior cruciate ligament (ACL) reconstruction [16]. Average pain scores evaluated at 6 and 24 hours following reconstructive surgery confirmed that the gabapentin arm experienced significantly lower mean pain scores (4.8 at 6 hours on a 10cm scale) in comparison to the placebo group (6.9 at 6 hours on a 10cm scale) [16].

We propose a novel use of oral gabapentin administered in conjunction with paracervical block for surgical abortion, and believe that its use in this setting will reduce intraoperative and post-operative pain. Gabapentin 600mg was selected as a well-tolerated intermediate dosage with benefit proven in prior preoperative studies. Multiple post-operative doses in addition to the pre-operative dose had no significant effect on VAS scores at 24 hours, thus favoring single dosage [9]. Gabapentin will be given 1-2 hours preoperatively. A 100-mm pain visual analog scale has been shown to be useful for the evaluation of pain in prior pain abortion research [7, 18], with a 30% difference on a 100 mm-VAS scale, or 13-mm to 22-mm difference, as clinically meaningful [19, 20] [25].

1.3 Design and Methodology

1.3.1 Research design and General Methodology Approach

This is a randomized double-blind placebo-controlled trial evaluating the impact of gabapentin given preoperatively on perioperative pain scores for women receiving a surgical abortion. Randomization will be done using computer generated random Fellowship in Family Planning Research Proposal Outline

numbers. Allocation concealment will be maintained by identically labeled sealed sequentially numbered pill containers. Gabapentin and placebo will be packaged in identical gelatin capsules and sealed by an independent pharmacy. Gabapentin and placebo gelatin capsules will be indistinguishable by appearance, thus maintaining double blinding.

Primary study outcomes: Our primary outcome measure will be pain score using a 100-mm visual analog scale (VAS) measured intraoperatively at time of evacuation.

Secondary outcomes: We will also be measuring pain on the 100-mm VAS preoperatively immediately prior to the procedure, at completion of the procedure (removal of the speculum), 10 minutes and 30 minutes following the procedure, and at discharge. Nausea and vomiting will be assessed during the same time intervals using a 100-mm VAS scale. Anxiety prior to the procedure will be measured using the preoperative state trait anxiety inventory. Side effects will be assessed using a checklist prior to discharge. We will also be contacting participants on post-operative day 1 to assess pain, nausea, vomiting, side effects and general satisfaction with the procedure (on a 5-point scale). The quantity and type of medications used perioperatively and post-operatively, including medications used at home in the 24 hours post-operatively, will be abstracted from the clinical record and assessed on the phone. Outcome measures will be collected on a tablet using a web-based password-protected relational database (REDCap). All VAS scale scoring and questionnaires will be completed using this database on a research-designated tablet.

Baseline Characteristics and Covariates:

We will collect baseline demographics, medical history (gravidity, parity, prior abortions (medical and surgical), gestational age, drug and alcohol use, psychiatric or sexual assault history, medications used at home and given at the clinic preoperatively, and indication for procedure (personal/social, fetal, or maternal health). This information will also be obtained using a research-designated tablet.

Outcome measures and baseline variables are described in table 1.

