1.3.5 Admission procedure

After financial clearance, all participants who have opted for a surgical abortion with local anesthesia will be approached for interest in the study. A study interest card will be placed on their medical chart, and the participant will be accompanied by the financial counselor and taken to the designated research room. This designated research room is a private room located in AWC. The study team will then review the recruitment script with the patient. If the patient is interested in the study, then a member of the study team will consent the participant. Following consent and enrollment into the study, the participant will be taken to the clinical nurse. The nurse will review the participant's chart to ensure eligibility for surgical abortion and gabapentin administration. The participant will then receive the study drug or placebo. Following administration of the drug, the participant will return to the designated research room. The study staff will review the baseline questionnaire that includes demographic questions. Following completion of the questionnaire, the participant will continue to wait in the designated research room or preoperative area. One hour after the administration of the drug or placebo, the participant's chart will be placed back into rotation for surgical procedures. The study team will accompany the participant to the clinical lounge where they will gown and prepare for the procedure. The participant will then undergo the procedure in order of chart placement. Prior to initiating the abortion procedure, study staff will administer the preoperative questions. Staff will administer the intraoperative questions at the time of evacuation during the uterine aspiration, and at time of removal of the speculum at the end of the procedure. Immediately following the procedure, the study staff will follow the participant to the recovery room to complete the remaining questions assessed at 10 minutes, 30 minutes and at discharge. Per clinic protocol, patients remain in the recovery room for approximately 30-60 minutes after surgical abortion with local anesthesia. When the discharge questions are complete, the participant will receive a \$30 gift card and be reminded to expect a follow-up call the following day (post operative day #1).

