1.3.10 Data analysis

We will compare groups on the primary continuous outcome measure (pain score on 100-mm point VAS) using T-tests and Mann-Whitney U test. Chi-square and T-tests will be used to evaluate secondary outcomes for categorical and continuous variables, respectively. Baseline characteristics will be evaluated for potential interaction or confounding with primary and secondary outcomes.

All available data from completed questions will be used for analysis, including partially completed surveys. Participants may request that their data not be used for analysis if a request is received prior to analysis as mentioned in the consent form. A statistician will be consulted to assist with the analysis as needed.

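### No pre-dose pain, nausea or anxiety score is described, so the unadjusted comparisons give up precision, mainly for the nausea and anxiety secondary outcomes

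*Combined protocol and SAP*

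**What the plan says.** **Timing of the capsule.** Section 1.2: "Gabapentin will be given 1-2 hours preoperatively". Section 1.3.5 orders the visit as consent, nurse review, capsule, baseline questionnaire, then a hold: "One hour after the administration of the drug or placebo, the participant's chart will be placed back into rotation for surgical procedures". After that, "Prior to initiating the abortion procedure, study staff will administer the preoperative questions".

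**Timing of the scores.** Section 1.3.1 on pain: "We will also be measuring pain on the 100-mm VAS preoperatively immediately prior to the procedure". On nausea: "Nausea and vomiting will be assessed during the same time intervals using a 100-mm VAS scale". On anxiety: "Anxiety prior to the procedure will be measured using the preoperative state trait anxiety inventory". Table 1 lists all three preoperative measures as secondary outcomes.

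**What is collected as baseline.** Section 1.3.1 and Table 1 list demographics, obstetric and medical history, medications, expectation of pain and pain with a prior abortion. Neither list includes a current pain, nausea or state anxiety score. The questionnaire forms themselves are not in the text available for review.

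**Order of forms.** Section 1.3.5 places the baseline questionnaire after the capsule. Section 1.3.6, under withdrawals and losses, says that all intake forms are finished before randomisation, which comes just before the pill.

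**Analysis.** Section 1.3.10 compares the primary outcome by t-test and Mann-Whitney test. For the rest: "Chi-square and T-tests will be used to evaluate secondary outcomes for categorical and continuous variables, respectively". Baseline characteristics are to be examined for interaction or confounding, but no adjusted model is specified.

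**The concern.** Less nausea and less anxiety are stated hypotheses and secondary aims in section 1.1.2. Both states can differ a good deal between women on arrival, before any drug is given. Without an arrival score, that variation stays in the error term. An arm difference in preoperative nausea or anxiety also cannot be checked against where the arms started.

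There is a second hazard. A score labelled preoperative looks like a baseline and invites use as a covariate. The pain and nausea scores with that label are taken when the drug may already be acting, so adjusting for them could remove part of any gabapentin effect. The plan does not rule this out. A pre-dose score cannot be recovered once the capsule has been taken.

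**Working it through.** **1. Are the first scores post-dose?**

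- Pain: taken just before the procedure (1.3.1). The chart re-enters rotation only "One hour after the administration of the drug or placebo" (1.3.5). The first score is therefore at least an hour post-dose.
- Nausea: same time points as pain, so the same conclusion.
- Anxiety: measured once, before the procedure. If it belongs with the preoperative questions, it is at least an hour post-dose. If it sits in the baseline questionnaire, it is post-dose by less than an hour under 1.3.5. If it is an intake form, it is pre-dose under 1.3.6. The first reading is the most natural, because the score is called preoperative and listed as an outcome, but it is an inference.

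**2. The plan's own sample size (1.3.11).** Inputs: difference 15 mm, SD 26 mm, 80% power, alpha 0.05 (two-sided reproduces the figure), 1:1 allocation assumed.

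- Per arm: 2 × (1.960 + 0.842)² × 26² / 15² = 47.2, rounded up to 48, so 96 in total.
- 96 / 0.864 = 111.1, stated as 111.
- 111 × 1.2 = 133.2, stated as 133.

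All three figures reproduce. None relies on covariate adjustment.

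**3. Gain from a pre-dose covariate.** If the pre-dose score has correlation rho with the outcome, adjustment multiplies the residual variance by (1 − rho²). The standardised effect d becomes d / √(1 − rho²). Power is from the noncentral t, two-sided 5%, with all 133 women analysed (67 and 66) and one degree of freedom spent on the covariate. The documents give neither rho nor an effect size for nausea or anxiety, so both are assumptions.

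Worked case, d = 0.4 and rho = 0.5: 0.4 / √0.75 = 0.462. Dividing by √(1/67 + 1/66) = 0.1734 gives noncentrality 2.66, against 2.31 unadjusted.

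| rho | Power, d = 0.4 | Detectable at 80% power |
|---|---|---|
| 0 | 62.9% | 0.489 SD |
| 0.3 | 67.0% | 0.467 SD |
| 0.5 | 75.3% | 0.424 SD |
| 0.7 | 89.4% | 0.350 SD |

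**4. Sensitivity to the assumed effect.** At rho 0.5 the gain is 5.4 points for 0.2 SD (20.8% to 26.2%), 12.4 for 0.4 SD and 4.8 for 0.6 SD (93.0% to 97.8%). So 0.4 SD lies near the peak. At rho 0.3 the gain is at most about 4 points for effects from 0.2 to 0.7 SD.

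**5. Primary outcome.** d = 15/26 = 0.577. Power at 133 is 91.0% unadjusted, 91.3% at rho 0.1, 92.1% at 0.2 and 93.3% at 0.3. Resting pain before dosing may be low in most women and only weakly related to pain at suction, so 0.1 to 0.2 is a cautious assumption. The gain is then 0.3 to 1.1 points.

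**The case against.** The strongest reply is that nothing here is invalid. Randomisation protects the unadjusted tests, the sample size needs no adjustment, and the powered outcome gains almost nothing. The benefit falls on secondary outcomes and depends on correlations that nobody has supplied. A nausea scale with many zeros would not follow the normal-theory power figures closely. More forms before dosing also add load in a clinic where flow is a stated concern (project summary and section 1.6). All of this stands, and it makes the point an inexpensive improvement rather than a defect.

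A reader might infer more than the documents support in four ways:

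- *That anxiety is certainly scored an hour or more after the capsule.* No section says so. The conflict over form order does not rescue the design, however. If the one inventory is pre-dose, it cannot show a drug effect on anxiety; if it is post-dose, it has no baseline.
- *That no outcome has any pre-dose counterpart.* Medication use has a partial one, because home and preoperative clinic medications are recorded. If the trait scale is used (1.3.1 names a state trait inventory, Table 1 a state inventory), it could serve as a partial covariate.
- *That imbalance between arms cannot be examined at all.* Age, parity, gestational age, psychiatric history and pain with a prior abortion are collected, and 1.3.10 promises a look at confounding. These help, but they do not replace an arrival score of the same measure.
- *That the nausea aim rests on one comparison.* Nausea is scored repeatedly through discharge and again on day 1, and Table 1 adds vomiting episodes.

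**Conclusion.** The point holds as a loss of efficiency and interpretability, not as bias. It is firm that the first pain and nausea scores come at least an hour after the capsule, that no pre-dose pain, nausea or anxiety score is described, and that the named tests are unadjusted. The anxiety timing is inferred.

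The gain could be useful for nausea and anxiety if their pre-dose scores correlate about 0.4 to 0.5 or more with later ones: at 0.4 SD, power is 70.5% at rho 0.4, a gain of 7.6 points. It is modest at 0.3 and negligible for the primary at 0.1 to 0.2. These figures assume 1:1 allocation, all 133 women analysed and roughly normal scores.

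**What to change.** - **Form order.** Reconcile sections 1.3.5 and 1.3.6 on whether intake and baseline forms come before or after the capsule, and state when the anxiety inventory is given.
- **Section 1.3.5.** Collect one pain VAS, one nausea VAS and the state anxiety items on the study tablet before the capsule. Keep the later preoperative scores as outcomes.
- **Section 1.3.10, secondary outcomes.** Analyse the continuous nausea and anxiety outcomes and the secondary pain scores with a linear model on arm and the pre-dose score of the same measure.
- **Section 1.3.10, primary outcome.** Keep the stated t-test and Mann-Whitney test, and add the adjusted model as a supporting analysis.
- **Covariate rule.** State that scores taken after the capsule are not used as covariates.

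The cost is a minor amendment, a few extra minutes before dosing and slight participant burden, which matters somewhat given the concern about clinic flow. No extra participants or staff are needed.

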1.3.2 Criteria for the selection of subjects

Location:

This study will take place at Atlanta Women's Center (AWC), a free-standing abortion clinic in metro-Atlanta that offers abortion services to women up to 23 weeks 6 days gestation.

This clinic operates 4 days per week (Wednesday through Sunday) with a clinical volume of 15 to 45 abortions per day. As abortion services are limited in the southeastern region of the United States, women often travel from other states, including Tennessee, Alabama, Florida,

Mississippi, North Carolina and South Carolina to receive care at this clinic. Approximately 4800 women are seen annually at AWC, with 720 women having abortions under local anesthesia and 3740 women receiving deep sedation anesthesia. Approximately 3320 women are 6-12 weeks GA, 800 women are 13-18 weeks and 340 women are over 18 weeks. Based on the patient volume, we do not anticipate any difficulty in recruiting patients to complete this study within the timeline presented. Misoprostol for cervical preparation is given prior to cases at 10 to 14 weeks per provider preference. Local anesthesia is offered as an option up to 16 weeks, however most cases performed with local anesthesia are less than 14 weeks, with the later gestational ages performed with deep sedation.

AWC, where [name] is the medical director and the study will be conducted, has documented success in participating in and recruiting for several industry sponsored and investigator initiated research studies: a randomized trial of levonorgestrel compared to

Table 1: Outcome measures and covariates	
Primary outcome	
Pain score validated on a 100mm VAS scale measured at time of start of uterine evacuation
Secondary outcomes:	
Pain on VAS scale: preoperatively, completion of procedure (removal of speculum), 10 and 30 min following procedure in the recovery room, at time of dischargeMedication use: pain and nausea medication used during and after procedureNausea/vomiting: pre op and post op nausea per VAS and episodes of vomitingAnxiety: preoperative state anxiety inventorySide effectsPostop assessment via phone on POD#1: pain, nausea, vomiting, and overall clinic experience

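### Perioperative anxiety is a stated secondary aim, but the only anxiety outcome described is a preoperative inventory, and its timing relative to the study capsule is not fixed

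*Combined protocol and SAP*

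**What the plan says.** The Project Summary, under Proposed research, states: "we hypothesize that gabapentin will reduce nausea, vomiting, anxiety, and consumption of pain medication". Section 1.1.2 repeats this with a wider time frame: "we hypothesize that pre-operative gabapentin will reduce perioperative nausea, vomiting, and anxiety". The same section lists "Perioperative anxiety" among the secondary aims, next to perioperative nausea and vomiting.

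Section 1.3.1 then gives the measure: "Anxiety prior to the procedure will be measured using the preoperative state trait anxiety inventory". Table 1 (section 1.3.2) also lists a preoperative inventory as the anxiety outcome, although it names a state inventory where section 1.3.1 names a state-trait one.

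For the neighbouring outcome in the same aim, section 1.3.1 says: "Nausea and vomiting will be assessed during the same time intervals using a 100-mm VAS scale". That refers to the pain time points before the procedure, at speculum removal, at 10 and 30 minutes and at discharge. The day-1 call in Table 1 covers "pain, nausea, vomiting, and overall clinic experience". The day-1 list in section 1.3.1 has no anxiety item either.

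On the sequence of the day, section 1.3.5 puts the capsule first, then the baseline questionnaire, then a wait of at least one hour, and then: "Prior to initiating the abortion procedure, study staff will administer the preoperative questions". Section 1.3.6 says that randomization follows completion of all intake forms and comes immediately before the capsule is taken.

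**The concern.** The aim covers a longer period than the measure does. Section 1.1.1 gives anxiety as a reason for the trial because it shapes the woman's experience of the abortion and her return to normal activity. Section 1.2 cites earlier outpatient surgical evidence that gabapentin reduces anxiety. A reader of the final report will expect an answer that includes the procedure and recovery.

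If the plan is followed as described, a null comparison could be reported as no effect on perioperative anxiety, although the procedure and recovery were not assessed. A positive one could be taken to cover periods for which no score is described. No analysis can later recover a score that was not collected.

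The second problem is timing. If the inventory were completed before the capsule, even the pre-procedure comparison would say nothing about the drug.

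**Working it through.** No figure in the plan bears on this point, so the check sets the stated aim against the described schedule.

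**Step 1: time points described** (section 1.3.1 and Table 1, checked against sections 1.3.5 and 1.3.6)

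| Time point | Pain | Nausea | Anxiety |
|---|---|---|---|
| Before the procedure | yes | yes | inventory |
| Evacuation | yes (primary) | not clearly stated | none described |
| Speculum removal | yes | yes | none described |
| 10 minutes | yes | yes | none described |
| 30 minutes | yes | yes | none described |
| Discharge | yes | yes | none described |
| Day 1 | yes | yes | none described |

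Pain has 7 time points: 1 before, 1 during and 5 after. Nausea has 6: 1 before and 5 after, or 7 if evacuation is counted. Anxiety has 1, before the procedure.

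**Step 2: what perioperative means here.** Section 1.1.2 uses the word for nausea, vomiting and anxiety together, and nausea is scored before and after the procedure. The same section hypothesises a reduction in perioperative pain, and the primary measure of pain is taken during evacuation. In this protocol the word is therefore wider than preoperative.

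**Step 3: when the inventory is completed.** The text does not say which form holds it. There are three possibilities:

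- It is among the intake forms. Section 1.3.6 places these before randomization, so the score is pre-dose. The expected difference between randomised arms is then zero whatever the drug does.
- It is in the baseline questionnaire. Section 1.3.5 places this after the capsule and before the one-hour wait ends, so the score is post-dose but early.
- It is among the preoperative questions. Section 1.3.5 returns the chart to rotation one hour after the capsule and asks these questions just before the procedure. The score is then at least one hour post-dose, and the comparison between arms is a valid test of an effect on pre-procedure anxiety.

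The documents do not settle which of these is intended.

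**The case against.** The strongest reply has three parts.

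First, perioperative includes preoperative. If the inventory follows the capsule, comparing pre-procedure anxiety between randomised arms is a sound test of part of the aim. This stands. A reader might infer that the anxiety aim cannot be tested at all, and the documents do not support that. The shortfall is in coverage.

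Second, the contents list names separate forms for the intraoperative, immediate post-operative, 10-minute, 30-minute, discharge and 24-hour assessments, and a quality-of-recovery survey. None of these is in the supplied text. The survey is also absent from section 1.3.1 and Table 1, so those lists do not describe every instrument. This also stands. A reader might conclude that none of the 133 women will have any anxiety data during or after the procedure, but that is more than the text shows. What it shows is that no such outcome is described. An item on an unseen form, with no place among the outcomes, would still leave the aim without a defined measure.

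Third, the outcome is already labelled as preoperative, which limits over-reading, and the number of time points for a secondary outcome is partly a matter of preference. The label helps, but it conflicts with the aim and hypothesis as worded, and one of the two has to change.

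Two further inferences are tempting and should not be drawn. The documents do not say that the score is taken in the waiting area. The 2-hour time to peak concentration in section 1.3.4, set against a procedure from one hour after dosing, applies equally to the preoperative pain and nausea scores, so it is not an argument about anxiety in particular.

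**Conclusion.** The mismatch holds. A secondary aim and hypothesis concern perioperative anxiety, and the one outcome described for it is preoperative: 1 time point, against 7 for pain. The described measures can answer only the pre-procedure part of the aim, and only if the inventory is completed after the capsule, which the text leaves open.

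The conclusion rests on the outcome lists in section 1.3.1 and Table 1 and on the procedures in sections 1.3.5 and 1.3.6. The unseen forms could add an item but could not by themselves make it a defined outcome. The primary outcome, the sample size of 133 and the main analysis are not affected. This is an inexpensive improvement to a secondary aim that should be made. It does not threaten the trial's main result.

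**What to change.** 1. Keep the preoperative inventory as the pre-procedure anxiety outcome. State that it is given with the preoperative questions of section 1.3.5, after the capsule and immediately before the procedure. Name the same instrument in section 1.3.1 and Table 1.
2. Add one short state-anxiety item, for example a 100-mm VAS, to the existing tablet assessments before the procedure, at speculum removal and at 30 minutes. List it in Table 1 and compare it between arms as a secondary outcome. It should supplement the inventory. A lone 30-minute score in its place would again rest on one time point and would miss the procedure.
3. If no item is added, restrict the anxiety aim and hypothesis in the Project Summary and section 1.1.2 to pre-procedure state anxiety, so that no claim is made about the procedure or recovery. Step 1 is still needed.

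The cost is a few seconds of extra questioning at each of three assessments that already take place, a short amendment, and more secondary comparisons: four for anxiety (the inventory plus three item scores) in place of one. No extra visits, staff or participants are needed. The third option costs only a change of wording.
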